11.4.4 SAFETY ANALYSES

For the safety primary endpoint of percent time in range < 70 mg/dL, the calculation is as follows:

(# of glucose values in range < 70 mg/dL/total number of all glucose values) * 100

This result will be presented as median and interquartile range (25-75).

Each AE or SAE will be independently reported as percent of patients experiencing the event. SAE's that require stopping the study prematurely will be separately reported in a table. If the principal investigator feels the AE or SAE's are secondary to the intervention this will be reported in the final study summary. Any rescue medicine that is used per 8.5.1 will be separately reported as percent of subjects requiring rescue medicine.

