4 RISK/BENEFIT ASSESSMENT

4.1 KNOWN POTENTIAL RISKS

The main risk associated with tight glucose control studies is hypoglycemia, with hypoglycemia being defined as any glucose value less than 70 mg/dL. The rate of hypoglycemia has traditionally been close

DEMONSTRATION OF AN ARTIFICIAL INTELLIGENCE BASED CLOSED LOOP GLUCOSE CONTROL SYSTEM AS A THERAPEUTIC MODALITY IN TYPE 1 AND TYPE 2 DIABETIC PATIENTS

Protocol IMT 2022-1

CONFIDENTIAL

Version1.0.7

22 August 2022

to 20% in studies aiming at lower glycemic targets.^{77,78} In addition, hypoglycemia in tight glucose control studies has been associated with increasing mortality rates,^{14,18} although a causal relationship has not been established. The immediate risk of a hypoglycemic event, especially a clinically important one with glucose values less than 54 mg/dL, is impaired brain function resulting in a temporary coma, or a hypoglycemia induced seizure.^{79,80} However, there does not appear to be any long term cognitive impairment in adults who have experienced hypoglycemic events.^{81,82} An additional potential risk of tight glucose control is the development of hypokalemia, which can lead to a prolonged Qt interval and potentially fatal dysrhythmias. However, this issue has been reviewed and it was found that there was no association found between tight glucose control and development of prolonged Qt syndrome.^{83,84}

Hypoglycemia is a risk for any tight glucose control study, however the AI based FUSION glucose control system under study was particularly effective at avoiding hypoglycemic events in the simulation and animal studies. When the control range was set to 100-140 mg/dL in the simulation studies, no glucose values less than 70 mg/dL were recorded in either study. In the two subject first in human study the percent time in range less than 70 mg/dL was zero.

The risks of severe hypoglycemia (< 54 mg/dL); moderate hypoglycemia (54 – 69 mg/dL) with associated hypoglycemia symptoms of anxiety, irritability, sweating, hunger, shakiness, fatigue, pale skin, lethargy, seizures; and symptoms of hypoglycemia at any level due to falling glucose levels (e.g., neuroglycopenia) will be mitigated by the following means:

1. Monitoring of the subject's glucose level with two Dexcom G6 CGM's.
2. Sharing of the Dexcom G6 CGM's values with study personnel via the Dexcom Follow App on two smartphones.
3. Setting the Dexcom CGM's to alarm for CGM glucose values less than 85 mg/dL.

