7. Measure the percent of glucose values that are within the range of 70-180 mg/dL.

Statistics – No statistical comparison will be made for this measurement.

8. Measure the percent of glucose values that are within the hyperglycemic range of > 180 mg/dL.

Statistics – No statistical comparison will be made for this measurement.

9. Measure the mean glucose value in mg/dL.

Statistics – No statistical comparison will be made for this measurement.

10. Measure of dispersion – coefficient of variation.

Statistics – No statistical comparison will be made for this measurement.

11. The study data will be used to determine the percentage of paired glucose values (continuous glucose monitors and the average of the two continuous glucose monitors versus the Nova StatStrip Hospital Glucose Meter System Reference glucose) in each zone using a Clarke error grid analysis.¹ No statistical comparison will be made for this measurement.

The glucose data for the above statistical analysis will be the glucose data used by the FUSION system for purposes of glucose control, unless otherwise specified.

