11.2 SAMPLE SIZE DETERMINATION

As this is a first in human study of a medical device a statistically determined sample size was not used. Rather, the subject number of eight was chosen as it is consistent with the FDA's recommended number of 6-10 subjects for a first in human study of a medical device.

The anticipated dropout rate after subjects have begun closed loop glucose control is less than 10%, which should not significantly affect the study results. No interim analysis is planned. Given the small sample size no subgroup analysis is planned.

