11.4.3 ANALYSIS OF THE SECONDARY ENDPOINT(S)

For the secondary endpoints that measure percent time in range, the values will be calculated as noted above in 9.4.2. These results will be presented as median and interquartile range (25-75).

The number of hypoglycemic events less than 70 mg/dL will be presented as median and interquartile range (25-75).

The mean glucose level will be presented as mean \pm SD.

The coefficient of variation will be presented as median and interquartile range (25-75).

The Clarke error grid analysis will be presented as a graph of the Clarke error grid. The Reference Glucose Value (Nova StatStrip Hospital Glucose Meter System) and Dexcom G6 data will be analyzed to determine the percent of all values that are in zones A, B, C, D and E.

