11.4.7 SUB-GROUP ANALYSES

Not applicable.

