11.4.8 TABULATION OF INDIVIDUAL PARTICIPANT DATA

Not applicable.

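### Hypoglycemia endpoints are reported only as pooled median (IQR), so with 8 subjects one affected subject always gives a primary safety result of 0 (0-0)

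*Combined protocol and SAP*

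**What the plan says.** Section 11.4.2 calculates the percent of values below 70 mg/dL separately for each subject. Section 11.4.4 repeats this as the primary safety analysis and states: "This result will be presented as median and interquartile range (25-75". Section 11.4.3 applies the same summary to the other time-in-range endpoints, which include percent below 54 and percent 54-69. It adds: "The number of hypoglycemic events less than 70 mg/dL will be presented as median and interquartile range (25-75". Section 11.3 analyses everyone who starts closed loop control as one set. That set is planned as 2 type 1 and 6 type 2 subjects.

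The sections headed "SUB-GROUP ANALYSES" (11.4.7) and "TABULATION OF INDIVIDUAL PARTICIPANT DATA" (11.4.8) each contain only an entry of not applicable. Section 11.2 gives the reason for the first: "Given the small sample size no subgroup analysis is planned". For these endpoints the plan has no range, maximum or count of affected subjects, and it names no quantile definition.

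Section 11.4.4 has a second reporting route: "Each AE or SAE will be independently reported as percent of patients experiencing the event". Rescue medicine is also reported as a percent of subjects. A Reference Glucose Value below 54 mg/dL is a listed severe event in section 10.3.3.1 and a listed serious event in Attachment 1. The glucose endpoints use a different source. Section 11.1 states: "The glucose data for the above statistical analysis will be the glucose data used by the FUSION system for purposes of glucose control". That value is the average of the two CGMs.

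The synopsis and section 11.1 name both diabetes types. The primary objectives in section 5 name type 2 only.

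**The concern.** A median with quartiles says little about a variable that is zero for most of a small group. Zero is a plausible value here. Section 4.1 reports: "In the two subject first in human study the percent time in range less than 70 mg/dL was zero". Those two earlier subjects both had type 2 diabetes, so the two type 1 subjects are new to this system in humans.

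The study tests no hypothesis, so what it prints is its whole result. If the primary safety line reads 0 (0-0) both when nobody went low and when one subject spent hours low, it does not report safety. If affected subjects do show, a reader still cannot tell whether they were type 1 or type 2. That matters because the synopsis chose type 1 subjects for the difficulty of controlling them safely.

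**Working it through.** The plan gives no figure to reproduce. The sample size of 8 is chosen by convention (section 11.2) and no test is planned. The check is on what the stated summary prints.

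**Inputs.** n = 8, of whom 2 are type 1 and 6 type 2 (synopsis, section 6.1). There is one percentage per subject (11.4.2), summarised by median and 25th and 75th percentiles (11.4.3, 11.4.4). Let k subjects be affected, each with value v, and the other 8 - k be zero.

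**Position of the upper quartile.** Across the nine standard definitions the 75th percentile of 8 ordered values lies between the 6th and 7th. For example, the linear definition puts it at 1 + 0.75 × 7 = 6.25, Hazen at 0.75 × 8 + 0.5 = 6.5, and Weibull at 0.75 × 9 = 6.75.

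| Affected (k) | v | Median | Upper quartile |
|---|---|---|---|
| 1 | 1%, 10% or 100% | 0 | 0 under all nine definitions |
| 2 | 10% | 0 | 0 under three; 2.5, 5, 5, 5.62, 5.83 and 7.5 under the other six |
| 3 | 10% | 0 | 10 |
| 4 | 10% | 5 | 10 |

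- With k = 1 the 6th and 7th values are both 0, so v has no influence.
- With k = 2 the 6th value is 0 and the 7th is 10, so the answer depends on interpolation: linear gives 0.25 × 10 = 2.5, Weibull gives 0.75 × 10 = 7.5.
- For the event count, seven zeros and one subject with 6 events also give 0 (0-0).

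**Clinical scale.** Assume one value every 5 minutes for 24 hours, which is 24 × 60 / 5 = 288 values. Two hours below 70 is 24 values, and 24/288 = 8.3% for that subject. The planned display is still 0 (0-0).

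**Diabetes type.** Two affected subjects can be chosen in 28 ways: 1 pair both type 1, 2 × 6 = 12 mixed, and 15 both type 2. With equal values, all 28 give the same display.

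**Number analysed.** With one affected subject, 0 (0-0) is also certain at n = 7. At n = 6 it depends on the definition: the upper quartile runs from 0 to 2.5 for v = 10%.

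**Which lows the adverse event route misses.** The CGM Validation Criteria (8.1.1.4) allow a difference of 20 mg/dL from Reference when the CGM reads below 100. With both CGMs passing:

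- A FUSION value of 53 can go with a Reference value up to 53 + 20 = 73. That counts in the below-54 endpoint but is not the listed serious event.
- A Reference value of 53 can go with a FUSION value up to 73. That is the listed serious event but contributes nothing to the below-70 endpoint.

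Wider gaps are possible until a failing CGM is recalibrated.

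**What a count would show.** One affected of 8 is 12.5%, with exact 95% interval 0.3-52.7%. None of 8 has interval 0-36.9%.

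**The case against.** The strongest reply is that the lows are not really hidden. A Reference value below 54 and any rescue treatment are reported as a percent of subjects, and this stands. The general adverse event definition in section 10.3.1 is also broad enough that an investigator could record an asymptomatic 54-69 episode. Nothing requires it, however. Rescue medicine covers 54-69 only with symptoms (8.5.1). The snacks or juice offered for a Reference value below 70 are not clearly counted in 11.4.4. Protocol 2 calls for an adverse event form for defined hyperglycemic or ketotic events, with no equivalent stated for 54-69. The fair description is that the route is possible but not assured.

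Second, subject protection does not rest on this summary. Termination rules act on individual values, the Independent Safety Monitor sees individual data, and records are reviewed after each session. This is true and limits the harm to reporting. It does not change what the primary safety result will say.

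Third, masking is not certain. If three or more subjects are affected the upper quartile leaves zero, and if the entire study is terminated early (section 9.2) with six or fewer subjects, one affected subject may show. Two earlier subjects are thin evidence for mostly zeros. These points make masking possible rather than expected.

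Fourth, the absence of subgroup analysis is a reasoned choice. That holds for by-type summary statistics with two type 1 subjects, but eight labelled rows are a listing, and small numbers are the reason to give one. The sponsor's second animal study, described in section 3.2, took that approach in part: with 8 treated and 6 control animals, it reported how many had severe hypoglycemia (0 and 5) beside the medians.

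**Conclusion.** The concern holds. Followed as written, the plan gives a primary safety result of 0 (0-0) whenever exactly one of 8 subjects has values below 70, however many. With two affected, the result depends on an unstated quantile definition, and the median stays at zero with three affected. No planned output separates type 1 from type 2.

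The single-subject result is exact at 7 or 8 analysed subjects and needs no assumption about glucose. The 8.3% example assumes evenly spaced values. A Reference value below 54 remains visible through adverse event reporting. The gap is in FUSION-value lows outside that definition and in the primary endpoint itself. The type 2-only wording in section 5 is a lesser, separate inconsistency. This should be fixed before the data are reported, and confidence is high.

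**What to change.** - **Section 11.4.8:** replace the not-applicable entry with a listing of every endpoint for each of the 8 subjects, labelled by diabetes type.
- **Sections 11.4.3 and 11.4.4:** add the range (including the maximum), the total number of events, and the number of subjects with any value below 70 and any value below 54. Give these counts separately for the FUSION glucose value and the Reference Glucose Value. Keep median and IQR alongside, and name the quantile definition.
- **Section 5:** align the primary objectives with the synopsis and section 11.1 so that they name both diabetes types.
- **Optional:** an exact 95% interval for the overall count, and a count of subjects given oral carbohydrate for low glucose.

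The cost is one listing, a few table rows and a wording change. Per-subject percentages are already calculated (11.4.2), some are already given to subjects (10.1), and Reference values are already on the case report form (8.1.1.4). No extra patients are needed and no clinical rule changes. Only the oral carbohydrate count might need a new form field.

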Subjects will be allowed to have snacks between the hours of 2100 on day 1 and 0600 hours on day 2 of their CRC study, or at any time for CGM or Reference Glucose Values less than 70 mg/dL or for symptoms of neuroglycopenia. Subjects will preselect their breakfast, lunch, and dinner meal choices from the CRC menu prior to the study. These meals will be unannounced to the FUSION system. Once the closed loop glucose control period has ended after 24 hours of glucose control, the control software will be stopped, and the subject will be disconnected from all intravenous infusions.

If the subjects are removed from the study due to the occurrence of a severe hypoglycemic event (< 54 mg/dL), the subjects will have their glucose values measured with a Reference Glucose Analyzer (e.g., Nova StatStrip Hospital Glucose Meter System) every 10 minutes, until their Reference Glucose Values are greater than 70 mg/dL. They will then have additional Reference Glucose Values drawn every 30 minutes, until they have consistent Reference Glucose Values in the range of 80-250 mg/dL for a period of at least two hours. See *Recovery Period* (Pages 107-108) for details with regards to subcutaneous insulin doses to be received prior to discharge from the Clinical Research Center.

The insulin and dextrose 50 mL medication syringes may not be used for more than 24 hours. Although the study should be terminated after a period of 24 hours (e.g., may not go longer than 24 hours), if for any reason the study period is longer than 24 hours (e.g., on orders from the principal investigator), the insulin and dextrose medication syringes must be exchanged for new medication syringes. To be clear, the insulin and dextrose medication syringes may not be used for a period of time exceeding 24 hours.

8.1.1.6 VISIT 3, TIME 29 TO 32 HOURS (OBSERVATION AFTER CLOSED LOOP GLUCOSE CONTROL SESSION)

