8.5.1 RESCUE MEDICINE

The study site will supply rescue medication that will be obtained locally. The following rescue medications may be used:

1. 15 mL of 50% Dextrose for intravenous delivery (IV push), every 10 minutes as needed.
2. Glucagon (1 mg/mL) for Intramuscular or intravenous delivery. May give repeat dose 15 minutes after first dose.

The 50% dextrose and Glucagon rescue medications will be used to treat the following conditions:

- 1) Severe hypoglycemia, which is defined as a Reference Glucose Value less than 54 mg/dL.
- 2) Moderate hypoglycemia (Reference Glucose Value in the range of 54-69 mg/dL) that is accompanied by any of the following neurological signs of hypoglycemia: Anxiety, irritability, sweating, hunger, shakiness, fatigue, pale skin, lethargy, seizures.
- 3) Neuroglycopenia, which is defined as hypoglycemia of sufficient duration and degree to interfere with normal brain metabolism and function. Neuroglycopenia may occur at Reference Glucose Values greater than or equal to 70 mg/dL. If the subject has signs of hypoglycemia such as anxiety, irritability, sweating, hunger, shakiness, fatigue, pale skin, lethargy, or seizures, they will be treated with 15 mL of 50% Dextrose."

These medications will be hand pushed into the subject's intravenous line by the study nurse or given by intramuscular injection in the case of Glucagon. The date and time of rescue medication administration as well as the name and dosage regimen of the rescue medication will be recorded on the case report forms.

In addition to the above rescue medications, in cases of severe hypoglycemia, moderate hypoglycemia with hypoglycemia symptoms, or neuroglycopenia, the subjects will also be offered snacks and glucose containing juices to treat their hypoglycemia and related symptoms.

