11.1 STATISTICAL MEASUREMENTS

Primary Safety and Efficacy Endpoints:

1. Safety

The safety of the FUSION system will be determined by its ability to avoid hypoglycemia in adult type 1 and type 2 diabetic patients consuming three meals over a period of 24 hours. Safety will be measured by calculating the percent of all glucose values that are within the hypoglycemic range of less than 70 mg/dL.

Statistics – No statistical comparison will be made for this measurement.

2. Efficacy

The efficacy of the FUSION system will be determined by its ability to maintain glucose in the normal range in adult type 1 and type 2 diabetic patients consuming three meals over a period of 24 hours. Efficacy will be measured by calculating the percent of all glucose values that are within the normal glucose range of 70-180 mg/dL.

Statistics – No statistical comparison will be made for this measurement.

Secondary Efficacy Endpoints:

The secondary objectives of the study are to assess the controller's ability to minimize glucose curve measurements associated with increased ICU morbidity/mortality rates, and to maximize those measurements associated with decreased ICU morbidity/mortality rates.

1. Measure the percent of glucose values that are within the severe hypoglycemic range of 0- <54 mg/dL.

Statistics – No statistical comparison will be made for this measurement.

2. Measure the percent of glucose values that are within the moderate hypoglycemic range of 54-69 mg/dL.

Statistics – No statistical comparison will be made for this measurement.

3. Measure the number of hypoglycemic (< 70 mg/dL) events.

Statistics – No statistical comparison will be made for this measurement.

DEMONSTRATION OF AN ARTIFICIAL INTELLIGENCE BASED CLOSED LOOP GLUCOSE CONTROL SYSTEM AS A THERAPEUTIC MODALITY IN TYPE 1 AND TYPE 2 DIABETIC PATIENTS

Protocol IMT 2022-1

CONFIDENTIAL

Version1.0.7

22 August 2022

4. Measure the percent of all glucose values that are within the desired glucose control range of 100-140 mg/dL.

Statistics – No statistical comparison will be made for this measurement.

5. Measure the percent of glucose values that are within the range of 70-140 mg/dL.

Statistics – No statistical comparison will be made for this measurement.

6. Measure the percent of glucose values that are within the hyperglycemic range of > 140 mg/dL.

Statistics – No statistical comparison will be made for this measurement.

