11.3 POPULATIONS FOR ANALYSES

Not applicable. All subjects who begin closed loop glucose control will be used for analysis.

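### The plan's only count of outside hypoglycemia treatment leaves out juice and snacks, so some lows treated by staff would be reported as no rescue

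*Combined protocol and SAP*

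**What the plan says.** All references are to the combined protocol and SAP.

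- **Rescue summary (11.4.4).** "Any rescue medicine that is used per 8.5.1 will be separately reported as percent of subjects requiring rescue medicine". No other summary of outside treatment is planned.
- **What counts as rescue (8.5.1).** The rescue medications are 50% dextrose and glucagon. The section then adds that, for severe lows, symptomatic moderate lows and neuroglycopenia, "the subjects will also be offered snacks and glucose containing juices to treat their hypoglycemia and related symptoms". Its CRF instruction (date, time, name, dosage) is written for the rescue medications only.
- **When oral carbohydrate may be given.** During closed loop, 8.1.1.4 permits glucose drinks, and 8.1.1.5 permits snacks, for a CGM or Reference value below 70 mg/dL or for neuroglycopenia. Section 8.1.1.5 also has a window that does not depend on glucose: "Subjects will be allowed to have snacks between the hours of 2100 on day 1 and 0600 hours on day 2".
- **Primary safety endpoint (11.4.4).** The percentage is the number "of glucose values in range < 70 mg/dL/total number of all glucose values) * 100". Sections 5 and 11.1 take these values from the glucose that FUSION uses for control, normally the average of two CGMs (4.3.1). No rule flags or handles values after treatment of a low.
- **Analysis set and presentation.** "All subjects who begin closed loop glucose control will be used for analysis" (11.3). Results are medians with interquartile ranges, and tabulation of individual participants is marked not applicable (11.4.8).

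**The concern.** Section 8.1.1.5 describes control as autonomous, and 11.1 judges safety by the system's ability to avoid hypoglycemia. A reader of the results will want to know how often staff had to step in. The only planned answer is the rescue-medicine rate, and the intervention with the widest trigger is outside it. With no hypothesis test and eight subjects, the descriptive tables are the whole of the evidence. A rescue rate of 0% could be read as the controller needing no help when subjects had been given juice for low readings. If the time and reason for oral treatment are not noted at the bedside, they may not be recoverable later.

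**Working it through.** There is no plan figure to reproduce. Section 11.2 says that "a statistically determined sample size was not used", and for each primary endpoint 11.1 says "No statistical comparison will be made for this measurement".

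**Step 1: which staff treatments reach the rescue rate.** Closed loop running, IV access in place:

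| Situation | Oral carbohydrate | Dextrose or glucagon | In rescue rate? |
|---|---|---|---|
| Reference <54 | offered (8.5.1) | yes (4.1, 8.5.1) | yes |
| Reference 54-69 with listed symptoms | offered (8.5.1) | yes (4.1, 8.5.1) | yes |
| Reference 54-69, no symptoms | allowed (8.1.1.4, 8.1.1.5); offered (Protocol 2, step 19) | not indicated in 8.5.1 | no |
| One CGM <70, Reference 70 or above, no symptoms | allowed (8.1.1.4, 8.1.1.5) | not indicated in 8.5.1 | no |
| Neuroglycopenia relieved by juice within 10 minutes, Reference 70 or above | offered (4.1, 8.5.1) | no under 4.1; yes under 8.5.1 | depends on the section followed |

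The third and fourth rows are the clear gap. The fifth exists only if 4.1 is followed.

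**Step 2: effect on the rate.** Input: 8 subjects (11.2), all starting closed loop. If k subjects receive only oral treatment and none receives dextrose or glucagon, the plan reports 0/8 = 0%. An any-treatment rate is k/8:
- k = 1: 1/8 = 12.5%
- k = 2: 2/8 = 25%
- k = 4: 4/8 = 50%

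**Step 3: can a treated low be absent from the endpoint?** The trigger can be one CGM or a Reference value, whereas the endpoint uses the average. Take assumed readings of 65 and 85 mg/dL. The average is (65 + 85)/2 = 75, so the endpoint has no value below 70, yet a snack is allowed because one CGM is below 70. Each CGM differs from the average by 10/75 = 13.3%, under the 20% discrepancy alarm in Protocol 2, step 17. If the average stays at 70 or above, this low appears in neither the percentage, the event count nor the rescue rate.

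**Step 4: values after treatment.** CGM values arrive every 5 minutes (4.3.1), so 24 h gives 24 × 60/5 = 288 values, each worth 100/288 = 0.347%. Episode lengths are assumptions, because the documents give none:
- untreated low of 30 min: 6/288 = 2.08%
- untreated low of 60 min: 12/288 = 4.17%
- untreated low of 120 min: 24/288 = 8.33%
- ended by treatment at 10 min: 2/288 = 0.69%
- ended by treatment at 20 min: 4/288 = 1.39%

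The formula treats oral carbohydrate, dextrose and glucagon alike: values after any of them stay in numerator and denominator.

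**Step 5: the planned summary.** With eight subjects the median is the mean of the fourth and fifth ordered values. If three or fewer subjects have any value below 70, both are 0 and the median is 0, however long those lows lasted.

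**The case against.** The strongest reply is that a reader might infer more than the text supports, namely that leaving juice out of the rescue count makes the primary safety endpoint wrong. It does not. The formula keeps values after every kind of treatment, so relabelling juice as rescue would leave the primary result unchanged. That part of the reply stands in full.

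Other points also stand:

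- FUSION values below 70 before the carbohydrate acts still count. The number of events below 70 and the percentages at 54-69 and below 54 are separate endpoints. Juice can shorten an event already in the FUSION data but cannot erase it.
- Reference values are taken every 10 minutes once a CGM or Reference value is below 70 (Protocol 2, step 15) and are recorded on the CRF (8.1.1.4).
- Nothing shows that oral treatment will be the commonest intervention or will shorten every low. It is allowed or offered, FUSION infuses dextrose itself, and the two earlier subjects spent no time below 70 (4.1).
- Overnight snacks are not rescue. They are carbohydrate not announced to the controller and can also raise glucose and prompt insulin, so their effect on percent below 70 has no fixed direction.
- The CRF is not among the documents, so silence in the protocol does not prove that a field is missing. The SAE form asks about other steps taken, which gives oral treatment of a value below 54 a place to be recorded.
- The durations in Step 4 are arbitrary. If only one subject has a low, the planned summary is 0 (0-0) whatever its length.

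None of this closes the gap in the rescue rate. The last point also shows that the planned median would not reveal a treated subject.

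**Conclusion.** The point holds in a limited form. As written, the rescue rate omits oral treatment. Symptom-free lows of 54-69 mg/dL with IV access in place, and symptoms relieved by juice if 4.1 is followed, can be treated by staff and reported as no rescue. The effect on an any-treatment rate is 12.5 percentage points per such subject, assuming all eight start closed loop. Some lows treated on a single CGM or a Reference value may also leave no value below 70 in the endpoint.

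A separate matter is that percent below 70 reflects the controller plus any staff treatment, whether oral, intravenous or intramuscular. The documents give no expected frequency or duration of lows, so the size of that effect cannot be derived; Step 4 is illustration only. They do not support saying that the primary endpoint is invalid or that overnight snacks flatter it. This is a low-cost improvement in recording and reporting for a descriptive feasibility study.

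**What to change.** 1. In 11.4.4, beside the rescue-medicine rate, report the percent of subjects and the number of episodes with any hypoglycemia treatment (oral, IV or IM).
2. State that the CRF records, for each oral treatment, the time, the trigger value and its source (CGM or Reference), the reason and the carbohydrate amount. Record the time and amount of each overnight snack separately, so that it is not mistaken for treatment.
3. List percent below 70 by subject, flagging those with any outside-treated low, as a descriptive supplement. Leave the primary endpoint as defined.
4. Reconcile the passages on when snacks, juice and dextrose are given, so that a treated low is counted the same way throughout. Sections 8.1.1.4 and 8.1.1.5 use CGM or Reference below 70; Protocol 2, step 19 uses Reference below 70; 4.1 and 8.5.1 list severe lows, symptomatic moderate lows and neuroglycopenia, and differ on dextrose for neuroglycopenia. Which rule applies is for the investigators and sponsor to settle.

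The cost is one CRF line per treatment or snack, one or two table rows and an eight-line listing. No treatment needs to change for items 1 to 3. The downside is that the reported intervention rate may look less favourable.
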